1.0 INTRODUCTION

Each year in the United States, approximately 31,000 cases of kidney on upper urinary tract cancer occur, resulting in more than 11,900 deaths¹. These tumors account for approximately 3 percent of adult malignancies and occur in a male-female ratio of 1.5 is to 1. Although most cases occur in persons aged 50 to 70 years, renal carcinoma has been observed in children as younger 6 months. Between 1975 and 1995, a steady and significant increase in the incidence of renal carcinoma was seen, from 2 percent to 4 percent per year, and increase of 42 percent since 1973.

Surgery is the only known effective therapy for localized renal carcinoma. The standard procedure today for treatment of localized renal carcinoma is radical nephrectomy. Radical nephrectomy involves complete removal of Gerota's fascia and its contents, including the kidney and the adrenal gland, and provides a better surgical margin than simple removal of the kidney.

Laparoscopic nephrectomy is a less invasive procedure for the removal of kidneys with a small volume of RCC^{2,3,4}.

Radio surgical ablation of renal tumors offers a noninvasive alternative for treatment of renal malignancies. Radiosurgery is precisely delivered pinpoint radiation using an external stereotactic guidance and hypo-fractionated high-dose radiation in an attempt to ablate the kidney cancer.

In an initial preclinical evaluation, radiosurgery for extracorporeal renal tissue ablation was very promising and demonstrated its ability to ablate a targeted area precisely and completely with relative sparing of the surrounding tissue⁵.

Clinical experience with radiosurgery for renal tumors is limited. In a recent report⁶ 20 patients, age ranged from 31 to 85 years (mean 62), had 27 cancers treated with a volume ranging from 2.4 to 1366cc (mean 367cc). Patients were most commonly treated with 8 Gy times 5 fractions. The control rate was 93% with follow-up ranging from 2 to 45 months (mean 12 months). The survival or regrowth of tumor vasculature has been suggested to be a major determinant of radiation responses (Huang 2010 and Du 2012).

To evaluate each patient's prognostic potential we will measure MIF (both MIF-1 and MIF-2) and VEGF levels before and after radiation therapy to determine if these serum markers may give a predictive indication of tumor response.

2.0 OBJECTIVES

Primary objective: To evaluate and compare the clinical safety of utilizing four different schemes of radiosurgical ablative techniques for treating poor surgical candidates with renal tumors.

Secondary Objective: To evaluate and compare the clinical and radiographic efficacy of four different schemes of radiosurgical ablation of renal tumors in poor surgical candidates.

Serum Blood Marker Objective: To determine if serum markers collected before and after radiation may give a predictive indication of tumor response.

3.0 PATIENT SELECTION

Conditions for Patient Eligibility

- Patient is considered a poor surgical candidate for removal of renal mass as determined by anesthesiology pre-operative assessment or the surgical team, or medical team. (No major psychiatric illnesses.)
- Patient is ≥ 18 years of age.
- Patient is able to give and sign study specific informed consent.
- No prior radiation to the treatment field.
- Negative serum or urine pregnancy test within 72 hours prior to registration for women of childbearing potential.
- Patient has a radiologically and /or pathologically confirmed diagnosis of a renal tumor
- Karnofsky status of $\geq 60\%$
- Signed study-specific informed consent prior to study entry.

All/any clinical, radiological and pathological data for the patient will be reviewed and the study investigators will assess suitability for treatment with radio-surgical technique. If the eligibility criteria are met, the patient will be scheduled for a treatment planning session.

Conditions for Patient Ineligibility

- Any patient not meeting the eligibility criteria.
- Any patient with active connective tissue disease such as lupus, dermatomyositis.
- Any patient with active Crohn's disease or active ulcerative colitis.
- Major psychiatric illness, which would prevent completion of treatment or interfere with follow-up.

4.0 PRE-TREATMENT EVALUATIONS

- History and physical and KPS (Appendix 1).
- Patients have confirmed renal mass on imaging. The patients will be registered through the Seidman Cancer Center Clinical Trials Unit (CTU) in Oncore. Preoperative testing will be done to assess the patient's eligibility for radio-surgical treatment, locate the tumor, and evaluate its accessibility by this approach prior to the radiation treatment planning date.
- Imaging of the kidney will be obtained to evaluate the kidney prior to planning by CT or MRI of the chest and abdomen with or without contrast. Fiducial markers will be placed

prior to treatment, with consideration for repeat or initial biopsy. CT scan of chest and abdomen should be obtained for staging prior to treatment.

- Multiple percutaneous needle biopsies of the renal tumor will be obtained under radiological guidance. After the biopsies are obtained, 2-3 fiducials may be placed in or near the tumor via the 18 gauge needle, for image guidance purposes, alternatively, fiducial placement may be performed as a separate procedure in patients having pathology confirmed disease at the time of presentation for radiation therapy planning.
- It is preferable that the patient have their pathology review done at University Hospitals Cleveland Medical Center.
- All clinical, radiological and pathological data for the patient will be reviewed and suitability for treatment with radio surgical technique will be assessed. If the eligibility criteria are met, the patient will be registered in the study after obtaining informed consent.
- Radiological work up will be performed to evaluate for metastatic disease if clinically indicated.
- Radiological work up will be performed to evaluate baseline renal function prior to the start of radiation therapy if clinically indicated.

5.0 REGISTRATION PROCEDURES

Approximately 32 subjects will be enrolled onto this study; four to eight individuals will be assigned to one of four different categories for comparisons to be made; an additional series of 12 patients will be enrolled in groups of 4 and assigned to three different categories. Patients can be registered only after the eligibility criteria are met. In addition, the following information must be provided:

- Patient's name and ID number.
- Verifying Physician's Name.
- Demographic Data.
- Treatment planning and start date.
- Eligibility criteria information.
- Patient's consent to enroll in the study
- All eligibility source documentation and checklist will be sent to the CTU QA office for review prior to subject enrollment

6.0 RADIATION THERAPY

Patient will have a treatment planning session for delivery of radiosurgical treatments and an immobilization device will be custom made for every patient, per standard of care. Specification of patient immobilization for each radiation treatment will conform to institutional practice.

Serum Blood Markers:

Patients will be asked to participate in ELISA blood testing just prior to and immediately following each daily radiation therapy session. Approximately 5cc of blood will be collected

within 2 hours prior to and following completion of fractionated radiation therapy to assess the levels of MIF (both MIF-1 and MIF-2) and VEGF. This whole blood will be separated into plasma and rapidly frozen at -80 C using standard procedures. At later time points, plasma samples will be thawed and subjected to an ELISA for each of the markers using commercial kits and standards. Given that survival or regrowth of tumor vasculature has been suggested to be a major determinant of radiation responses, measurement of VEGF levels prior and following radiation, these tests may give a predictive indication of tumor response.

Pending patient approval, we will also store remaining plasma samples for detection of additional cancer markers to potentially improve our ability to predict for response to therapy with new tumor markers.

Radiation Doses:

Radiation will be delivered in 4 fractions. The initial dose level will be 6 Gy per fraction to a total dose of 24 Gy in 4 fractions. Doses will be escalated at 2 Gy per fraction increments to 12 Gy per fraction to a total dose of 48 Gy. The radiation treatment planning and evaluation details are appended.

Series I:

Twenty patients who are not surgical candidates will be offered treatment with a radio-surgical technique. Four patients will be registered in each dose group. Treatments will be initiated with 4 patients utilizing the minimum dose and observe what happens. If no DLTs are observed, then escalation to the next set of 4 patients to the next initial dose level will occur. If 1 DLT is observed, treatment of the next set of 4 patients at the same dose level will occur. If zero or 1 additional DLTs are observed, then dose escalation occurs as previously described. However, if $\geq 2/4$ or $\geq 3/8$ are observed at a given dose level the trial stops. On average, this results in between 4-5 patients being treated before escalation. The table below shows the probability of stopping giving an underlying toxicity level using this design.

Table: Probability of stopping escalation given underlying toxicity

Underlying Pr(Toxicity)	0.1	0.2	0.25	0.3	0.35	0.4	0.5	0.6	0.7	0.8	0.9
Pr(Stopping)	0.07	0.25	0.37	0.49	0.61	0.71	0.86	0.95	0.99	0.998	0.999

If a patient fails original treatment, he or she will be either kept on study for observation, or if they require retreatment, they will be taken off study.

Series II

The next series will be reached if insufficient dose limiting toxicities have occurred upon completion of the initial dose escalation series I to a total dose of 48 Gy in 4 fractions to warrant limitation of further dose escalation.

At this level, if normal tissue toxicities for SBRT have not proven to be problematic for renal lesions, then “standard” dose and fractionations will be prescribed for subsequent patients as would be used for example in Lung cancer. Given the 90% expectant local control for lung

lesions given 20 Gy in 3 fractions, we are highly anticipating reaching an efficacious dose during series II of the trial. If the 12 Gy x 4 fraction cohort is irradiated without dose limiting toxicities, then 12 additional patients will be accrued for further dose escalation following dose toxicity criteria defined below:

Based on the Linear Quadratic Model commonly used for radiobiologic comparisons, each subsequent group of four participants will receive further dose escalation using a 3 fraction regimen to increase beyond 48 Gy in 4 fractions in 20% dose equivalent increments.

The first group of four patients at this level (Series II) will receive 48 Gy to the target volume (tumor) in 3 fractions of 16 Gy per fraction. If acute toxicity is acceptable, then the next four patients will be escalated to 54 Gy in 3 fractions of 18 Gy. Finally if a dose limit has not been reached, the last group of four patients will be treated to 60 Gy in 3 fractions of 20 Gy each.

It is important to note that dose to the normal tissues surrounding the target has not been allowed to dose escalate. Tolerance levels selected for these normal organs (see Table I. and Appendix I., are consistent with RTOG standards and normal tissue limits approved for UHCMC Protocol Case 13807 associated with Prostate Cancer with Cyberknife or Linac based SBRT irradiation.

Table I. Dose Specifications for Normal Organs (and Appendix I.)

1. Bowel – No more than 1 cc can receive 8 Gy/fx for a total of 24 Gy in 3 to 4 fractions.
2. Cord – No more than 0.3 cc can receive 6.7 Gy/fx for a total of 20 Gy in 3 to 4 fractions.
3. Stomach - No more than 1.0 cc can receive 7.3 Gy/fx for a total of 22 Gy in 3 to 4 fractions.
4. Liver – No more than 2/3 of liver volume can receive 5.7 Gy/fx for a total of 17 Gy in 3 to 4 fractions. Additionally within that volume – 800 cc should not receive more than 5.0 Gy/fx for a total of 15 Gy in 3 to 4 fractions.
5. Contralateral Kidney- No more than 5 % of the volume can receive more than 4.7 Gy/fx for a total of 14 Gy in 3 to 4 fractions.

It is thought that superior Cyberknife or Linac based SBRT treatment plans and delivery for this current cohort may be achievable without any increase in normal tissue toxicity as defined above. If this is not the case for any of the 12 patients included in the new series of cohorts and where the treatment plan has been determined to fail, the patient target volume dose will be reduced to the previous cohort dose. In no case will a dose escalation occur if the normal tissue toxicities criteria are not met in the treatment plan.

If 3 successive patients fail to meet the treatment planning criteria, the dose escalation study effort will be terminated and successive remaining patients will be treated at target dose from the previous cohort of 4 patients.

For this second series of the study, patients who fail by evidence of tumor regrowth or metastatic dissemination will not be retreated to the current dose level. However, if the subject experiences

recurrence or progression, they will either be followed by observance; or if they require retreatment, they will be taken off study.

Radiation Toxicity:

All patients should be seen at 1, 3 and 6 months \pm 2 weeks, and then every 6 months by either the radiation oncologist or the urologist to evaluate radiation toxicities, or arranged to be seen locally if unable to return to Cleveland Medical Center with reports sent back for review. At 6 months post SBRT, the patient will be scheduled to be seen in Urology to evaluate their response to the therapy with imaging and an optional biopsy. Urinary and bowel irritation manifested as urgency, frequency, dysuria, infection and incontinence will be recorded. Medications to treat radiation side-effects will be recorded as well as dose and frequency. Acute Radiation Toxicity (<180 days from treatment date) will be documented using NCI common toxicity criteria, version 4.0. A shorter period of toxicity assessment for the purposes of dose escalation will be used. This will be done at the 1, 3 and 6 month follow-up visits after radiation therapy. More delayed short-term toxicities would be used in the final determination of the recommended Phase II dose.

Dose limiting Toxicity:

Acute Radiation Toxicity \geq grade 3 in the Gastrointestinal and renal/genitourinary categories of the common terminology criteria for adverse events 4.0 (CTCAE) will be considered dose limiting (see above). The maximum tolerated dose will be one dose level below which the adverse event, as described above, occurred (See statistical section).

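### Series II (16, 18 and 20 Gy x 3) has no stated DLT count for escalation, its two entry conditions part after 1 or 2 DLTs in 8 at 12 Gy x 4, and Section 9.0 is written for four levels only

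*Combined protocol and SAP*

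**What the plan says.** **Series I.** Section 6.0 gives a counted rule for 6, 8, 10 and 12 Gy x 4. No DLT in four patients escalates. One in four adds four more at the same dose, and up to one further DLT still escalates. At least 2 of 4, or at least 3 of 8, stops. A table gives the stopping probabilities. Section 9.0 repeats the rule for four cohorts of 4 to 8 and derives a maximum of 32 from four dose levels.

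**Entry to Series II.** Section 6.0 states it twice. First: "The next series will be reached if insufficient dose limiting toxicities have occurred upon completion of the initial dose escalation series I" to justify limiting further escalation. Then: "If the 12 Gy x 4 fraction cohort is irradiated without dose limiting toxicities, then 12 additional patients will be accrued". The same sentence announces the criteria that are to govern those patients: "for further dose escalation following dose toxicity criteria defined below".

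**Steps within Series II.** From 16 to 18 Gy x 3: "If acute toxicity is acceptable, then the next four patients will be escalated to 54 Gy in 3 fractions of 18 Gy". From 18 to 20 Gy x 3: "Finally if a dose limit has not been reached, the last group of four patients will be treated to 60 Gy". The text that follows gives organ dose limits and a stop after three successive treatment-planning failures.

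**DLT and MTD.** Section 6.0 defines a DLT as an acute gastrointestinal or renal/genitourinary event of grade 3 or higher. It continues: "The maximum tolerated dose will be one dose level below which the adverse event, as described above, occurred", and then points to the statistical section.

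**Size.** Section 5.0: "Approximately 32 subjects will be enrolled onto this study; four to eight individuals will be assigned to one of four different categories", plus a further 12 patients in groups of four over three categories. For Series I, Section 6.0 says: "Twenty patients who are not surgical candidates will be offered treatment with a radio-surgical technique".

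**The concern.** The toxicity criteria promised for Series II do not include a DLT count. The organ limits govern the planned dose, and the DLT definition says what counts as an event but not how many are tolerated.

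Two rules can be inferred:
- **4-then-8.** The MTD sentence refers to Section 9.0, whose rule speaks of the current dose in general terms. This is the better supported reading, although Section 9.0 names four cohorts and never mentions Series II.
- **0 of 4.** Groups of four totalling 12, set in Section 5.0 against four to eight per category in Series I, suggest no expansion. The MTD sentence read literally makes a single event limiting.

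Safety is the primary objective. With one DLT among the first four patients at 16 or 18 Gy x 3, one reading stops and the other treats four more and may escalate. The choice would be made after the toxicity is seen, and the MTD could not be reproduced from the plan.

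**Working it through.** **Inputs.** The rule and its table come from Section 6.0 (Series I), and the four-level scope and maximum from Section 9.0. The three groups of four come from Sections 5.0 and 6.0. The documents give no expected DLT rate, so p = 0.1, 0.2, 0.3 and 0.4 are assumed, the same at every level. This is illustrative, since risk may rise with dose. X and Y are independent DLT counts in groups of four, each binomial(4, p).

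**1. The plan's own figures.** Pr(stop) = P(X>=2) + P(X=1) x P(Y>=2).
- p = 0.1: 0.0523 + 0.2916 x 0.0523 = 0.0676 (plan 0.07)
- p = 0.3: 0.3483 + 0.4116 x 0.3483 = 0.4917 (plan 0.49)
- p = 0.4: 0.5248 + 0.3456 x 0.5248 = 0.7062 (plan 0.71)

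The other table entries agree to within 0.01, and 4 x 8 = 32. The Series I figures are correct.

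**2. The two inferable rules in Series II.** Both escalate on 0 of 4 and both stop on 2 or more of 4. They part only at exactly 1 of 4.
- 0 of 4: pass probability s = (1-p)^4
- 4-then-8: pass probability e = s + P(X=1) x P(Y<=1)

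For p = 0.2: s = 0.8^4 = 0.4096; P(X=1) = 4 x 0.2 x 0.8^3 = 0.4096; P(Y<=1) = 0.8192; e = 0.4096 + 0.4096 x 0.8192 = 0.7451.

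| Quantity | p=0.1 | p=0.2 | p=0.3 | p=0.4 |
|---|---|---|---|---|
| Exactly 1 DLT in 4, P(X=1) | 0.29 | 0.41 | 0.41 | 0.35 |
| Pass one level, 0 of 4 (s) | 0.66 | 0.41 | 0.24 | 0.13 |
| Pass one level, 4-then-8 (e) | 0.93 | 0.75 | 0.51 | 0.29 |
| Reach 60 Gy once Series II opens, 0 of 4 (s^2) | 0.43 | 0.17 | 0.06 | 0.02 |
| Reach 60 Gy once Series II opens, 4-then-8 (e^2) | 0.87 | 0.56 | 0.26 | 0.09 |

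**3. Entry.** The two conditions give different answers when 12 Gy x 4 passes with 1 or 2 DLTs in 8. Given that this level is reached, the probability is P(X=1) x P(Y<=1) = 0.28/0.34/0.27/0.16. Divided by e, that is 30%/45%/53%/56% of all passes at that level.

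**4. Size.** The overall maximum depends on the reading:
- entry on 0 of 4 and groups of four: 3 x 8 + 4 + 12 = 40
- entry after 1 or 2 DLTs in 8 allowed, groups of four: 4 x 8 + 12 = 44
- 4-then-8 at all seven levels: 7 x 8 = 56, of which up to 24 are in Series II

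Expected Series II size under 4-then-8, once it opens, is (4 + 4 x P(X=1)) x (1 + e + e^2). At p = 0.1 this is 5.166 x 2.802 = 14.5, and at p = 0.2 it is 5.638 x 2.300 = 13.0.

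**The case against.** The strongest reply is that the plan already leads to an answer. The DLT event is defined for all patients, the dose limit mentioned before 60 Gy naturally refers to it, and the MTD sentence sends the reader to Section 9.0. Read literally, that sentence would also contradict Series I, where 1 or 2 DLTs in 8 pass, so it is weak evidence for a 0-of-4 rule. All of this stands and favours 4-then-8. It does not settle the matter, because Section 9.0 confines itself to four cohorts and four levels.

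There are other safeguards. Section 6.0 holds the normal-organ limits constant as target dose rises, drops a patient to the previous dose if the plan fails, and ends escalation after three successive planning failures. Section 7.0 stops a patient's own radiation on a DLT, and Section 12.0 requires reporting to the toxicity committee and the IRB. These temper the risk, but none says whether the next four patients are treated.

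The figures are also conditional. With the same p throughout and the Series I rule for entry, Series II opens in only e^4 = 0.76/0.31/0.07/0.007 of trials, so the columns for p = 0.3 and 0.4 describe uncommon situations. That is fair.

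A reader might go further and infer three things that the documents do not support:
- **Escalation in Series II is unguided.** It is not: the event is defined, and both readings agree except at 1 of 4.
- **Twelve patients rule out expansion.** Series I also speaks of four per dose group and a total of twenty, yet expands to eight. Twelve may likewise be nominal.
- **The trial may breach its cap of 32.** Section 9.0 sets that figure for four levels, not for the whole trial. The 32 in Section 5.0 is approximate and can be read as 20 + 12.

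**Conclusion.** The plan is wrong as written on this point, within narrow limits. The outcome left undecided at each Series II level is exactly one DLT in four, which is common: 0.29 to 0.41 over the assumed rates. The choice of reading moves the chance of passing a level from 0.66 to 0.93 at p = 0.1 and from 0.24 to 0.51 at p = 0.3. The entry conditions are not contradictory in every case, but they disagree whenever 12 Gy x 4 passes with a DLT, and nothing says which governs. Section 9.0 omits the 12 Series II patients from its rule and its maximum; this is the lesser part.

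The sizes rest on the assumed constant DLT rates. That no count is stated does not depend on them. The point ranks between should-fix and must-fix, and it should be settled before Series II opens.

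**What to change.** State in Sections 6.0 and 9.0 that the Series I rule (0 of 4 escalates, 1 of 4 expands to 8, at least 2 of 4 or 3 of 8 stops) governs entry to Series II and each Series II level. The existing probability table then applies unchanged. To match:
- replace the two uncounted step conditions with this rule;
- reword the entry condition that requires no DLTs at 12 Gy x 4;
- tie the MTD sentence to the level at which the rule stops escalation, not to a single event;
- restate Section 9.0 for seven levels with a maximum of 56;
- in Section 5.0, label the approximate 32 as an expected total if 20 + 12 is meant.

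The cost is a text amendment with no new procedures, but Series II may need more than 12 patients: up to 24, with 14.5 expected at p = 0.1 and 13.0 at p = 0.2 once it opens.

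If the sponsor must hold Series II at 12, require 0 of 4 for both entry and escalation. Print the pass probabilities 0.66/0.41/0.24/0.13 for p = 0.1/0.2/0.3/0.4 and give a maximum of 40. This stops more often at a tolerable dose. At p = 0.1, counted from reaching 12 Gy x 4, 60 Gy is reached with probability s^3 = 0.28, against e^3 = 0.81 under the Series I rule. It also makes one DLT in four limiting at 16 Gy x 3 while 2 in 8 remains tolerable at 12 Gy x 4, which the protocol should acknowledge.

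### The per-fraction and total organ-dose limits in Table I agree only at 3 fractions; for the 4-fraction Series I regimen they differ by about one third and no rule says which governs

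*Combined protocol and SAP*

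**What the plan says.** Section 6.0 (Radiation Therapy), Table I, sets limits for five organs, with two limits for the liver. Each line links a per-fraction dose to a total and assigns the pair to both fraction counts:

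- Bowel: "No more than 1 cc can receive 8 Gy/fx for a total of 24 Gy in 3 to 4 fractions"
- Cord: "No more than 0.3 cc can receive 6.7 Gy/fx for a total of 20 Gy in 3 to 4 fractions"
- Stomach: "No more than 1.0 cc can receive 7.3 Gy/fx for a total of 22 Gy in 3 to 4 fractions"
- Liver, two-thirds of the volume: "can receive 5.7 Gy/fx for a total of 17 Gy in 3 to 4 fractions"
- Liver, second limit: "800 cc should not receive more than 5.0 Gy/fx for a total of 15 Gy in 3 to 4 fractions"
- Contralateral kidney, 5% of the volume: "can receive more than 4.7 Gy/fx for a total of 14 Gy in 3 to 4 fractions"

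Appendix I repeats the six limits with the same numbers.

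The Radiation Doses paragraph of section 6.0 states "Radiation will be delivered in 4 fractions" and takes the dose from 6 to 12 Gy per fraction, that is from 24 to 48 Gy in total. It refers the reader to appended details for planning and evaluation, and Appendix I is the only dose appendix. Series II then uses 3 fractions (16, 18 and 20 Gy each). So although Table I is printed within the Series II text, its lines name 4 fractions and cover the Series I patients too.

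**The concern.** Each line presents the per-fraction dose as adding up to the total. One pair of numbers cannot do that for both 3 and 4 fractions. If the pairs were derived for 3 fractions and then labelled for 3 or 4, every Series I patient is planned against a limit with two different values.

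At stake is the protection of normal organs in a trial whose primary objective is safety and whose dose-limiting toxicities are gastrointestinal and renal/genitourinary. Two planners reading the same line in good faith could apply organ limits one third apart.

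**Working it through.** **Inputs.** The six per-fraction limits *d* and stated totals *T* come from Table I, section 6.0. The fraction counts are 4 for Series I and 3 for Series II, also from section 6.0.

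**Step 1: reproduce the stated totals.** Implied total = *d* × number of fractions.

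| Limit | *d* (Gy/fraction) | Stated *T* (Gy) | *d* × 3 | *d* × 4 | Excess at 4 = (*d* × 4)/*T* − 1 |
|---|---|---|---|---|---|
| Bowel | 8 | 24 | 24.0 | 32.0 | 33.3% |
| Cord | 6.7 | 20 | 20.1 | 26.8 | 34.0% |
| Stomach | 7.3 | 22 | 21.9 | 29.2 | 32.7% |
| Liver, two-thirds volume | 5.7 | 17 | 17.1 | 22.8 | 34.1% |
| Liver, 800 cc | 5.0 | 15 | 15.0 | 20.0 | 33.3% |
| Contralateral kidney | 4.7 | 14 | 14.1 | 18.8 | 34.3% |

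At 3 fractions all six totals are reproduced to within 0.7%, and *T*/3 rounds to the printed per-fraction value every time. At 4 fractions none is reproduced. Since all six lines behave alike and the appendix repeats them, an isolated misprint or damage from text extraction does not explain the pattern.

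**Step 2: the same check in reverse.** Spread evenly over 4 fractions, the stated totals give *T*/4 = 6.00, 5.00, 5.50, 4.25, 3.75 and 3.50 Gy per fraction. These lie 24.7% to 25.5% below the printed per-fraction limits (bowel: 1 − 6.00/8 = 25.0%).

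**Step 3: does the difference matter at the doses prescribed?** Compare the limits with the first two Series I levels.

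- First level, 6 Gy × 4 = 24 Gy. The per-fraction figures for bowel, cord and stomach (8, 6.7 and 7.3 Gy) are above the prescribed fraction dose itself. The stated cord and stomach totals (20 and 22 Gy) are below the prescribed total.
- Second level, 8 Gy × 4 = 32 Gy. The per-fraction bowel figure equals the prescribed fraction dose. The stated bowel total is 24/32 = 75% of the prescribed total.

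So at these levels the same line may constrain a plan materially or hardly at all, depending on the figure used.

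**Step 4: look for a governing rule.** Neither section 6.0 nor Appendix I says that the total prevails, that the per-fraction figure prevails, or that both must be met.

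**The case against.** **The two figures can be read as joint caps.** A plan can satisfy both, and at 4 fractions delivered evenly the total would then always be the binding one. The higher totals of 32, 26.8 Gy and so on are printed nowhere, so a planner has to set aside a printed total to reach them. This is a reasonable reading and may be what was meant. But the protocol does not state it, and the wording presents the total as the sum of the fractions. The objection softens the point from two irreconcilable limits to two limits whose relation is not stated. It does not remove the ambiguity.

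**Not every 4-fraction patient would be affected.** This stands. The inconsistency is in the text for all of them, but only plans with organ doses between the two figures would be judged differently. How many such plans there would be is unknown.

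**The limits are tied to outside sources.** The protocol cites RTOG standards and another institutional protocol. Those might settle the 4-fraction reading, but they are not in the documents, and the planner should not have to infer the rule from them.

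A reader might also infer three stronger points, which the documents do not support:

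- *That the ambiguity drives dose reduction and early termination.* The rule that a failed plan lowers the target dose is written for the 12 Series II patients, and the rule on three successive failures is in the same Series II text. Series II uses 3 fractions, where the figures agree. Series I escalation depends on observed dose-limiting toxicities. The one link is a first-cohort Series II patient whose plan fails and who reverts to the previous cohort's dose. If that means the previous regimen, it is 48 Gy in 4 fractions, where the figures disagree.
- *That the statement "dose to the normal tissues surrounding the target has not been allowed to dose escalate" is contradicted.* If the totals bind, the physical limit is the same in both series. If the per-fraction figures bind, the permitted total falls by a quarter from 4 to 3 fractions. Neither is an escalation. An argument from biologically effective dose would need tissue parameters the documents do not give and a claim of equal biological effect they do not make; they invoke the Linear Quadratic Model for the target dose.
- *That toxicity comparisons between Series I levels are confounded.* All four levels share 4 fractions and the same lines of the table. Confounding would require planners to change their reading between cohorts, and nothing suggests that they would.

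**Conclusion.** The point holds as an internal inconsistency in the organ-dose limits for the 4-fraction regimen. All six limits are consistent at 3 fractions only. At 4 fractions the two figures differ by 33 to 34% of the stated total, or equivalently by about 25% of the per-fraction limit, and nothing in the documents says how to resolve the difference.

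The size is that of the gap between the two readings, not an estimate of excess dose delivered to anyone. The conclusion assumes that Table I and Appendix I apply to Series I, which rests on the lines naming 4 fractions and on the reference to appended planning details. It assumes nothing about which figure was intended.

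The consequence is confined to the acceptance or rejection of 4-fraction plans, including the Series II fallback case. Because these limits protect normal organs, the text should be corrected even though the number of plans affected cannot be estimated.

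**What to change.** The study team must reconcile the per-fraction and total figures in Table I and in Appendix I. Three changes to the text would do it:

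1. State the limits separately for the 4-fraction and the 3-fraction regimens.
2. Say which figure decides whether a plan meets the limit, or that both must be met.
3. Say which regimen's limits apply if a first-cohort Series II patient reverts to the previous cohort's dose.

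No view is taken on which value is right; that is for the study team to settle. The sentence on non-escalation of normal-tissue dose need not change on this account.

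The cost is an amendment to one table and its copy in the appendix. It needs no extra patients, procedures or analyses.
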